IVFE reduction (IFER) during the administration of neonatal parenteral nutrition will lead to a significant decrease in the rate of rise of direct bilirubin (mg/dL/week) when compared to standard therapy.

Secondary Hypotheses

1. The time to development of PNAC, when present, will be longer with IFER when compared to standard IVFE therapy.
2. IFER will not be associated with a significant increase in failure to thrive (as assessed by growth parameters) or the development of essential fatty acid deficiency (EFAD) when compared to standard IVFE therapy.
3. Neurodevelopmental outcomes (NDOs), when assessed at 12 and 24 months of corrected gestational age, will be similar for those treated with IFER and standard IVFE therapy.

Specific Aims

1. To determine whether neonates and infants receiving PN with IFER (1 g/kg/day) will have lower rates of rise of direct bilirubin compared to those receiving standard IVFE therapy (3 g/kg/day)
2. To compare the time to development of PNAC in neonates and infants receiving PN with IFER (1 g/kg/day) compared to those receiving PN with standard IVFE administration (3 g/kg/day)
3. To determine if IFER results in normal growth and essential fatty acid (EFA) parameters by measuring weight, length, head circumference (weekly) and EFA profiles (every 2 weeks in the IFER group) during the treatment period.
4. To compare NDOs at 12 and 24 months of corrected gestational (± 2 weeks) age of those treated with IFER with those treated with standard IVFE doses using a combination of neurodevelopmental screening tools (e.g. Bayley Scales of Infant Development, MacArthur Communicative Development Inventory, etc.) aimed at capturing several developmental domains such as motor, cognition, speech and language, sensory, and behavior.

Study Definitions

Subjects will be considered “on treatment” from the time of randomization until 7 days after PN has been discontinued, but not to exceed a total of 84 days. Subjects will be considered “on study” until they complete their neurodevelopmental testing at 24 months corrected gestational age (± 2 weeks).

Study Design

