This is a multi-institution, prospective, randomized study evaluating IVFE dose reduction on the development of PNAC as a proxy measure of PNALD in neonates requiring prolonged PN. The definition of PNAC will be that used predominantly in the literature – a direct bilirubin level of ≥ 2 mg/dL, documented on two occasions 1 week apart, in patients who have required parenteral nutrition for more than 2 weeks. **Eligible neonates will be randomized into two treatment arms: standard IVFE administration (3 g/kg/day) or IVFE reduction (IFER) (1 g/kg/day).** A total of 60 subjects (30 subjects per arm) will be included in the study. The study will evaluate

short- and long-term outcomes of this strategy. In the short-term, infants will be followed for up to 12 weeks for the development of PNAC. If a subject's PN is discontinued before 12 weeks, and if they remain in the hospital, follow-up data will be collected for an additional 7 days but not beyond a total of 84 days. Only standard-of-care data will be collected during these 7 days. No procedures will be performed for the purpose of this study during these 7 days. In the long-term, subjects' neurodevelopmental outcomes will be assessed at 12 and 24 months corrected gestational age (± 2 weeks).

Primary outcome measure:

1. The rate of rise of direct bilirubin as a function of time (mg/dL/week) between the two groups over 12 weeks or until the subject has been off of PN for >7 days, whichever comes first.

Secondary outcome measures

1. Initial 12 week period:
 - a. The incidence of PNAC (direct bilirubin ≥ 2 mg/dL) and severe PNAC (direct bilirubin ≥ 4 mg/dL in subjects on parenteral nutrition for at least 2 weeks)
 - b. The time to development of PNAC and severe PNAC
 - c. The peak total and direct bilirubin levels
 - d. The incidence of EFAD
 - e. Adequacy of growth as evaluated by z-scores for weight, height, and head circumference
 - f. Other safety measures assessed during the initial 12 week period will include adverse events (e.g., episodes of sepsis and catheter-related blood stream infections).
2. Long-term follow-up:

Neurodevelopmental assessments will include:

 - a. At 12 months corrected gestational age (± 2 weeks):
 - i. Bayley Scales for Infant and Toddler Development (BSID-III)
 - b. At 24 months corrected gestational age (± 2 weeks):
 - i. Bayley Scales for Infant and Toddler Development (BSID-III)
 - ii. MacArthur-Bates Communicative Development Inventories (CDI)

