 - iii. Brief Infant Toddler Social Emotional Assessment (BITSEA)
 - iv. Gross Motor Function Classification System (GMFCS)
 - v. Behavioral Assessment System for Children-Second Edition (BASC2)

Study Arms:

[figure not shown]
Study Arm 1 (Standard IVFE dosing): Subjects in the standard IVFE dosing arm (3 g/kg/day) will be on treatment for a total of 12 weeks or until the subject has been off of parenteral nutrition for >7 days, or if they are discharged from the hospital, whichever comes first.

Study Arm 2 (IFER dosing): Subjects in the IFER dosing arm (1 g/kg/day) will be on treatment for a total of 12 weeks or until the subject has been off parenteral nutrition for >7 days, or if they are discharged from the hospital, whichever comes first.

All subjects will be maintained at their assigned dosing regimen for the duration of the treatment period (12 weeks) or until they are transitioned off of PN for >7 days, are discharged or until the direct bilirubin is ≥ 2.5 mg/dL for 2 consecutive weeks, whichever occurs first. Data will be collected for the duration of the study for those subjects who remain on parenteral nutrition for the full 12 weeks. For those who transition off of PN prior to the end of the 12 week period, data will be collected for 7 days after termination of PN if the subject remains in the hospital. The clinical course of these subjects who wean off PN prior to 12 weeks will continue to be monitored according to standards of practice. If serum direct bilirubin reaches a level of ≥ 2.5 mg/dL for 2 consecutive weeks during the course of the treatment, subjects will be transitioned to an IVFE dose of 1 g/kg/day three days per week. Those who remain cholestatic at the termination of their treatment period will be evaluated on a monthly basis for the persistence or resolution of cholestasis. This will be done by obtaining monthly liver function tests and bilirubin fractions for 6 months.

Overview of Study Design:

Study Design

Inclusion Criteria

Study subjects will be neonates and infants who are ≥ 28 weeks corrected gestational age at the time of enrollment who are parenteral nutrition naïve (<72 hours of PN exposure prior to randomization) and whose direct bilirubin has never been >2 mg/dL with at least one of the following diagnoses:

1. Meconium ileus and peritonitis
2. Gastroschisis
3. Omphalocele >4 cm in diameter or with liver herniated outside of the abdominal cavity

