3. Weight, gestational age at the time of enrollment/randomization, and weekly thereafter
4. Inclusion diagnosis
5. Number of septic episodes according to standard definitions³⁸
6. Use of choleric medications
 - a. Ursodiol
 - b. Cholecystokinin
 - c. Phenobarbital
7. Nutritional data
 - a. Parenteral nutrition data
 - i. IVFE dose
 - ii. Dextrose infusion rate
 - iii. Total calories and % calories obtained via PN
 - b. Enteral nutrition data
 - i. Total calories and % calories being obtained via enteral route
 - ii. % calories obtained via breast milk
8. Growth parameters (whenever possible, obtain all growth measurements on the same day of the week)
 - i. Weight (with z-score) weekly (every 7 days ± 2 days)
 - ii. Height (with z-score) weekly (every 7 days ± 2 days)
 - iii. Head circumference (with z-score) weekly (every 7 days ± 2 days)
9. Additional safety data to be obtained from human subjects is summarized below, indicating any key differences in frequency of monitoring between the two groups:

Laboratory Parameter	Frequency (+24 hours)*
Fractionated bilirubin panel (includes total, indirect, and direct bilirubin)	One time weekly (Monday)
Serum bile acids (total)	One time monthly (every 4 th Monday on treatment)

Point of care or serum glucose measures	- Daily for the first 5 days of PN, then twice weekly (Monday, Thursday) - Confirmatory test if serum glucose is >150 mg/dL on electrolyte panel
Serum Triglycerides	One time weekly (Monday)
Essential Fatty Acid Profile	IFER Group: Every 2 weeks (Thursday) Standard Group: At the time of restriction of IVFE to 1 g/kg/day three days per week, then every 2 weeks (Thursday)
Comprehensive metabolic panel	Twice weekly (Monday, Thursday)
Magnesium level	Twice weekly (Monday, Thursday)
Phosphorus level	Twice weekly (Monday, Thursday)
Complete blood count	One time weekly (Monday)

* Lab draw volumes will be below each institution's daily limits

Definition of Sepsis

Sepsis will be defined in a standard manner using the following criteria (**Table 2**):³⁸

The presence of at least two of the following four criteria ***in the presence of or as a result of suspected or proven infection***:

1. Core temperature of >38.5C or <36C

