All adverse events will be graded as follows in their relation to IFER: definitely not related, unlikely to be related, possibly related, definitely related or insufficient information. All cases rated as possibly or definitely related will be defined as an SAE. These SAEs will be reported to the University of Michigan Sponsor-Investigator within 48 hours. The site PI will be contacted immediately and the case will be evaluated for reporting to IRB, FDA and study termination, if deemed necessary. Each clinical site will report SAEs to their local IRB as per their standard reporting policy. As per 21 CFR 312.32(c), the sponsors will also notify FDA and all participating investigators in an IND safety report of any adverse experience associated with the use of the drug that is both serious and unexpected.

Data Safety Monitoring Board

An independent data safety monitoring committee will be established to monitor the study for safety and to determine if a statistical difference has been achieved between the two groups for the primary outcome measure at interim data analyses. The data safety monitoring committee will review the data at the halfway point of the study to assess the safety and efficacy of the study to that point. If safety issues are revealed the study investigators and each site's IRB will be notified immediately. The data safety monitoring committee will also ensure that adverse events are promptly reported to the FDA, and all participating investigators will be notified as well of any adverse experience associated with the use of the drug that is both serious and unexpected.

Sample Size Determination

The sample size was calculated for the primary outcome (rate of rise of direct bilirubin) using previously published data as well as our clinical experience.^{22,23} We have assumed that the mean bilirubin levels at baseline, 4 weeks, 8 weeks and 12 weeks in the standard dosing group (2-3 g/kg/day) will be 0.55 mg/dL, 1 mg/dL, 1.5 mg/dL and 2 mg/dL corresponding to a slope of 0.125 mg/dL/week over 12 weeks. The standard deviation of the bilirubin measures at each of these four time points is 1. Likewise, we have estimated that the mean bilirubin levels at baseline, 4 weeks, 8 weeks and 12 weeks in the minimization group (1 g/kg/day) will be 0.45 mg/dL, 0.5 mg/dL, 0.45 mg/dL and 0.5 mg/dL (a slope of roughly zero). The standard deviation of the bilirubin measurements at

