each of these four time points is 1. The correlation of any two adjacent measures on the same individual is 0.5. This correlation drops to 0.354 between baseline and 8 weeks and to 0.25 between baseline and 12 weeks.

Using the above assumptions, a sample size of 15 subjects per group using a repeated measures ANOVA will have 85% power to detect the change in slopes as being significant at the 0.05 level, 79% power to detect a difference in means overall between groups and 88% power to detect the general change in means over time across the two groups. When the sample size is increased to 20 subjects per group, the above power numbers increase to 95%, 90% and 96%, respectively. If 30 subjects are recruited per group this design will allow for a 33% attrition rate by twelve weeks as we expect that not all patients will require PN for the full 12 weeks of the initial study period. Thus, we will recruit a minimum of 30 subjects per group to ensure adequate power to detect our primary outcome measure.

Of the secondary outcomes, sample size was also calculated for the incidence of cholestasis. Assuming an incidence of 50% in the standard group and an incidence of 10% in the minimization group, with $\alpha = 0.05$ and power of 80%, a sample size of 23 is required for each group. Regarding the other secondary outcomes, our sample size is large enough to allow for establishing trends which may then highlight avenues for future research.

Planned Statistical Analysis

All data analysis will be directed and performed by a statistician through the Center for Statistical Consultation and Research at the University of Michigan (<http://cscar.research.umich.edu/about/>). Data will be analyzed using SAS software release 9.3 for Windows (Copyright, SAS Institute Inc., SAS and all other SAS Institute Inc. product of service names are registered trademarks or trademarks of SAS Institute Inc., Cary, NC, USA). All study subjects will be included in the statistical analysis in an intent-to-treat manner.

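### The bilirubin-triggered lipid reduction falls mainly on the standard arm and stays in the primary slope, so the slope can understate the 3 vs 1 g/kg/day contrast in Aim 1; no planned slope analysis addresses this

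*Combined protocol and SAP*

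**What the plan says.** All references are to the combined protocol and SAP.

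- **Switch rule (Study Arms).** It applies to both arms. After two consecutive weeks at or above 2.5 mg/dL, "subjects will be transitioned to an IVFE dose of 1 g/kg/day three days per week".
- **Follow-up continues.** The primary outcome is "The rate of rise of direct bilirubin as a function of time (mg/dL/week) between the two groups over 12 weeks", ending earlier only when the infant has been off PN for more than 7 days. Study Definitions does not end the on-treatment period at the switch. The laboratory table under Data Collection starts fatty acid profiles for this event: "Standard Group: At the time of restriction of IVFE to 1 g/kg/day three days per week".
- **Aim 1 (Specific Aims)** asks whether IFER at 1 g/kg/day gives "lower rates of rise of direct bilirubin compared to those receiving standard IVFE therapy (3 g/kg/day".
- **Primary model (Primary Outcome Measure).** This is a linear mixed model with random intercept and slope, analysed by intent to treat. The paragraph has no dose term and no provision for the switch.
- **Dose as a covariate.** Average or mean IVFE dose is named in the Cox models, the count models for PNAC, severe PNAC and EFAD, and the neurodevelopmental analyses. Potential Confounding Variables lists the 2.5 mg/dL level among the causes of dose variation. It says the analysis will account for dose differences through mean dose and IVFE/IFER duration, without saying whether this includes the primary slope.
- **Power (Sample Size Determination).** For 15 per group the slope power is 85%. "When the sample size is increased to 20 subjects per group, the above power numbers increase to 95%, 90% and 96%, respectively", the first figure being the slope comparison.

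**The concern.** A standard-arm infant who meets the trigger goes from 3 g/kg/day to an average of 3/7 = 0.43 g/kg/day, which is less than the IFER arm receives. The infants affected are those with the highest bilirubin, and the planning means place most of them in the standard arm. If their bilirubin then falls, the standard-arm slope flattens because of rescue. A small slope difference could be read as showing that lipid dose matters little, when part of the explanation is that the worst-affected standard-arm infants no longer received the standard dose.

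The remedy mentioned for dose variation, adjustment for mean dose and duration, conditions on quantities fixed after randomisation, largely set by arm, and lowered by high bilirubin itself.

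**Working it through.** **1. The plan's power figure.** Inputs: standard-arm means, "in the standard dosing group (2-3 g/kg/day) will be 0.55 mg/dL, 1 mg/dL, 1.5 mg/dL and 2 mg/dL" at weeks 0, 4, 8 and 12; IFER means 0.45, 0.5, 0.45 and 0.5; SD 1; "The correlation of any two adjacent measures on the same individual is 0.5", then 0.354 and 0.25 at 8 and 12 weeks. A group-by-time F test with Geisser-Greenhouse correction (noncentral F approximation) gives 86.0% at 15 and 95.1% at 20 per group, against 85% and 95% stated. The companion figures also agree: 79.6%/90.2% for group (stated 79%/90%) and 88.9%/96.5% for time (stated 88%/96%). Attrition: 20/(1 − 0.33) = 29.9, so 30. The figure is reproduced, with no stated allowance for a switch.

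**2. How unequal the trigger is.** The chance that a single value is at least 2.5 mg/dL is 1 − Φ((2.5 − mean)/1).
- Week 8: standard 1 − Φ(1.0) = 16%; IFER 1 − Φ(2.05) = 2%.
- Week 12: standard 1 − Φ(0.5) = 31%; IFER 1 − Φ(2.0) = 2%.

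The rule needs two consecutive weekly values, so the weekly correlation matters, and the plan does not give it. Means were interpolated to 13 weekly values, and infants had to satisfy the eligibility condition "whose direct bilirubin has never been >2 mg/dL" at baseline. Three correlation models consistent with the stated values were used, with 1-week correlation 0.65 (from 0.5^((L/4+1)/2) at lag L weeks), 0.84 and 0.875. A random-slope model was run as a fourth.
- Switched before week 12: 21-25% standard and 2-4% IFER under the three correlation models; 18% and 1% under random slopes.
- Median switch in the standard arm: about week 10 under the 0.65 and random-slope models.

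**3. Effect on the slope difference.** This needs an assumed course after the switch. The plan's background section reports −0.73 mg/dL/week after restriction in an earlier study, but in established PNAC and on a twice-weekly regimen, so it is taken as the strong end. Differences are in mg/dL/week; ratios are to the no-effect row, from unrounded values.

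| Course after switch | 0.65 correlation model | Ratio | Random-slope model | Ratio |
|---|---|---|---|---|
| No effect of switch | 0.1211 | 1.00 | 0.1201 | 1.00 |
| Plateau | 0.1140 | 0.94 | 0.1164 | 0.97 |
| −0.25 per week | 0.1035 | 0.85 | 0.1094 | 0.91 |
| −0.5 per week | 0.0966 | 0.80 | 0.1025 | 0.85 |
| −0.73 per week | 0.0926 | 0.77 | 0.0973 | 0.81 |

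Starting the post-switch course from the infant's observed value, under the three correlation models, gives no reduction for a plateau and 10-27% at −0.3 to −0.73. Taken together: 0-6% for a plateau and roughly 10-27% for a fall of 0.3 to 0.73 per week.

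**4. Power with the switch.** With 30 enrolled per arm, one third leaving between weeks 3 and 11, and a mixed model, simulated power is 97-99% without a switch, at least 95% with a plateau, 86-98% at −0.3 and 81-92% at −0.73.

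**5. Mean dose as a covariate.** Average the dose over the 13 weekly points, with the assigned dose through the switch week s and 3/7 afterwards: standard-arm mean = [3(s+1) + (3/7)(12−s)]/13.
- s = 10: (33 + 0.86)/13 = 2.60.
- s = 2, the earliest possible when baseline is at most 2 mg/dL: (9 + 4.29)/13 = 1.02.

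The most an IFER infant can have in this coding is 1.00, so the arms do not overlap. (The coding ignores the standard-arm ramp-up, holds for triglycerides, and increases for growth or EFAD.) Results:
- As a main effect, mean dose moves the slope difference by at most 0.002.
- As a predictor of the slope, it moves the arm coefficient to between −0.218 and +0.462, against a true 0.12. Even when the switch has no effect on bilirubin, the coefficient becomes 0.166 (0.65 model) or 0.462 (random slopes), because high bilirubin lowers mean dose.

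**6. Values up to the trigger only.** With the covariance known, a likelihood analysis returns 0.1196 (0.65 model) and 0.1199 (random slopes). A fitted random-intercept-and-slope model gives 0.118-0.131, against about 0.121.

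**Limit.** With means of 0.45-0.5 and SD 1, a normal model makes Φ(−0.45) to Φ(−0.5), or 33% to 31%, of IFER values negative. Trigger rates are therefore approximate.

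**The case against.** The strongest reply is that the target may be the strategy. The primary hypothesis compares IFER with standard therapy, Study Design speaks of evaluating a strategy, and the background says practitioners often cut the dose once PNAC appears. On that reading rescue belongs to the comparison and the intent-to-treat slope answers the question. This reading is reasonable, and it is why the primary analysis should stay. It does not supply a slope estimate for the contrast as Aim 1 words it.

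Second, PNAC incidence and time to PNAC use 2 mg/dL, below the trigger, so they are largely fixed before any switch. That stands: they help interpretation, and the Kaplan-Meier comparison needs no dose covariate. They are secondary and do not estimate a slope.

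Third, the planning means rest on published data and clinical experience and may already be net of dose cuts. This cannot be checked from the documents. If they are, the reductions computed here do not apply against the plan's figures.

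Fourth, a reader might infer that dose adjustment will reverse the primary result. The documents do not support that: the primary-model paragraph lists no dose term, and no section proposes a dose-by-time interaction, which the reversal needs. What stands is that the general sentence under Potential Confounding Variables leaves the primary model's covariates open.

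**Conclusion.** The point holds as a matter of interpretation and pre-specification. The intent-to-treat slope validly compares the two dosing strategies including rescue. As an estimate of the contrast in Aim 1, it can be too small by the amounts in the working. That conclusion depends on an assumed response to the switch, an assumed weekly correlation, and planning means that are not already net of dose cuts. With no response to the switch there is no understatement. The direction, towards no difference, matters most if the observed slope difference is small.

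Two stronger readings are tempting. One is that the 95% power is wrong or the trial underpowered: the figure reproduces, and simulated power for the planned design stays at 81% or more even at −0.73 mg/dL/week. The other is that keeping post-switch data makes the primary test invalid: it does not, because the rule is the same in both arms and is part of the randomised strategies.

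Mean dose and duration do not solve the problem. They either leave the slope difference almost unchanged or, if allowed to predict the slope, can distort it.

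**What to change.** Keep the intent-to-treat primary analysis, the clinical rule and the sample size. Make two additions to the analysis plan:

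1. Pre-specify one supplementary mixed-model slope analysis using direct bilirubin up to and including the second consecutive weekly value of at least 2.5 mg/dL. Report the number of infants switched and the week of switch in each arm.
2. State that mean IVFE dose and IVFE/IFER duration will not be covariates in the primary slope model.

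Weekly bilirubin and IVFE dose are already collected, so nothing changes for infants or sites. The cost is one extra analysis. It relies on missing-at-random after the trigger, which is plausible because the switch depends on recorded bilirubin. It may slightly overstate the no-switch difference: at the top of the simulated range, 0.131/0.121 = 1.08, about 8% high. Leaving dose out of the primary model also gives up adjustment for dose changes due to triglycerides or EFAD, which the plan expects to be rare.

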14. Hypoxic ischemic encephalopathy

Standard IV lipid dosing compared to IV lipid minimization for the prevention of PNAC/PNALD

15. Congenital defect of the brain
16. Major seizure disorder

Removal from Study Protocol After Initiation of Study

The following criteria may require study removal:

1. Parent or guardian request for removal
2. Transfer to a non-study hospital
3. Development of multiple nutritional problems which are unable to be managed (e.g. more than mild undernutrition, irreversible undernutrition, hyperglycemia, or hypertriglyceridemia refractory to intervention)
4. At the discretion of the PI

Informed Consent

Informed consent will be obtained from the parents or legal guardian of the child. Consent will be obtained in person whenever possible. In the rare circumstance that a parent or legal guardian cannot be present in person, consent will be obtained via telephone. We expect this to be an unusual occurrence as subjects can be randomized up to 72 hours after PN initiation.

Randomization

Subjects will be randomized within 72 hours of PN initiation. Stratified, equal within-center randomization will be performed after consent is obtained. Group assignment will be determined by a random permutation of blocks of randomly determined sizes of 2 or 4. Randomization will be stratified based on gestational age (<32 and ≥32 weeks gestation). Enrollment and randomization will occur as early as feasible after identification of subjects who meet eligibility criteria. Randomization MUST occur within 72 hours of PN initiation to minimize the number of days of PN prior to treatment group assignment. All subjects will be treated according to standard management until consent is obtained and randomization occurs. Once randomization occurs the PN dose the subject is currently on may change based on group assignment.

Blinding

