Descriptive statistics using standard statistical tests (e.g. Student's t-test, paired sample t-test, Wilcoxon rank sums tests, Fisher's exact tests, Chi-square test, McNemar's test, etc.) will be used throughout the statistical analysis of data. Logistic regression will be used to compare differences between groups. Because septicemia can exacerbate PNAC, we will include the incidence of septicemia as a covariate in our analysis. Septic episodes will be defined as positive cultures or clinical presentation consistent with sepsis during the 7 day period corresponding to the subject's weekly bilirubin value. The number of septic episodes will be accounted for using a Poisson regression analysis (or possibly a negative binomial regression if there is more variability than expected for a Poisson distribution), with the total time on PN as an offset, allowing us to compare the rate of occurrence of septic episodes in the two groups.

Primary Outcome Measure

The primary outcome measure – change in direct bilirubin as a function of time (mg/dL/week) between the two groups – will be evaluated using a linear mixed model analysis to compare the slope of total bilirubin levels between the standard and reduced groups. This model will allow us to examine the degree of variability between subjects in the rate of change over time, and will take this variability into account in the model by including a random effect for the slope of time for each subject as well as a random intercept for each subject.

Secondary Outcome Measures

1. Time to PNAC (direct bilirubin ≥ 2 mg/dL) and time to severe PNAC (direct bilirubin ≥ 4 mg/dL)

The time to development of a first occurrence of PNAC and of severe PNAC will be evaluated using survival analysis. Initially, we will compare the two groups using Kaplan-Meier curves, but the eventual analysis will take into account important covariates, such as development of sepsis, average IVFE dose and percentage of calories from enteral feeds using a Cox proportional hazards survival analysis. We will test whether the proportional hazards assumption is met for the analysis by including an interaction term between treatment group and time to see if any differences between the groups are consistent or increase/decrease over time. The effect of important time-varying covariates (e.g., septic episodes) can also be taken into account using a Cox model.

2. Level of peak total and direct bilirubin

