These measures will be compared between the two treatment groups using a linear mixed model.

3. Incidence of PNAC, severe PNAC, and EFAD

The number of occurrences of each of these outcomes will be compared using either a Poisson regression model or a negative binomial model if the variance in these counts is greater than expected for a Poisson distribution. We will also include the time on TPN as an offset, so that we can compare the rates of occurrence of each of these outcomes for the two treatment groups. These regression models will be adjusted for the covariates such as development of sepsis, average IVFE dose, and percentage of enteral feeds.

4. Adequacy of growth as evaluated by z-scores for weight, height and head circumference

The z-scores for each of these measures will be compared between the two treatment groups using a linear mixed model. For normally growing infants, we would expect that there would not be a trend in z-scores because we would expect them to maintain their curve. However, for the subjects in this study, there may be a loss in z-score over time due to inadequate growth. The slopes of the changes in these z-scores over time will be compared between the two treatment arms. A random intercept will be included for each subject to allow for individual variability in average values as well as a random slope to allow for variability in the rate of change over time across subjects. Important covariates, such as gestational age (<32 weeks gestation vs. ≥32 weeks gestation) and birth weight will also be used as covariates in this analysis.

5. Neurodevelopmental Outcomes

Bayley Scales of Infant and Toddler Development (BSID-III):⁴⁵ Raw scores are converted to composite and subscale scores using age-standardized norms. Scale composite average internal consistency reliability coefficients range from .91 to .93 with subtest reliability ranging from .86 to .91. Validity-related studies indicate relatively high correlations (.72-.79) with the Wechsler Preschool and Primary Scale of Intelligence – Third Edition (WPPSI-III)⁵³ and with the Preschool Language Scale – Fourth Edition (PLS-4)(.71-.83).⁵⁴

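### The primary slope model names neither randomisation stratum; adding gestational age and its interaction with time would protect precision if bilirubin slopes differ by stratum

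*Combined protocol and SAP*

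**What the plan says.** The Randomization section sets two factors. On centre: "Stratified, equal within-center randomization will be performed after consent is obtained". On gestational age: "Randomization will be stratified based on gestational age (<32 and ≥32 weeks gestation". Blocks are of size 2 or 4. The number of centres is not given.

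Under Primary Outcome Measure, the comparison of slopes between arms is to be made with a linear mixed model, "by including a random effect for the slope of time for each subject as well as a random intercept for each subject". Neither centre nor gestational age is named there. (The sentence refers to total bilirubin although the outcome is direct bilirubin; that is a separate matter.)

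Other covariates are named. Planned Statistical Analysis says "we will include the incidence of septicemia as a covariate in our analysis", and Potential Confounding Variables says that analyses will account for enteral intake and IVFE dose. None of these is a stratification factor.

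Elsewhere the plan does adjust for gestational age. The growth model uses the same cut: "Important covariates, such as gestational age (<32 weeks gestation vs. ≥32 weeks gestation) and birth weight will also be used as covariates". The neurodevelopment models also control for gestational age. Centre appears in no model.

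**The concern.** The plan adjusts for its gestational-age stratum in secondary analyses but not in the primary one, and it gives no reason. The Background section lists prematurity among the established risk factors for PNAC, so the protocol itself treats gestational age as prognostic.

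Stratified blocks make the arms similar in their mix of strata. If infants under 32 weeks have a different bilirubin slope, that difference contributes little to chance imbalance between arms. An unadjusted model still counts it as unexplained slope variance, so the reported standard error exceeds the true spread of the estimate. What is at stake is precision in a trial of 60 infants, of whom about 40 are expected to give 12-week data. A second point is prespecification: the text is silent, so adding the strata later would be a post-hoc choice on the primary test.

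**Working it through.** **1. Inputs (Sample Size Determination).** Means at weeks 0, 4, 8 and 12 are 0.55, 1, 1.5 and 2 mg/dL (standard) and 0.45, 0.5, 0.45 and 0.5 mg/dL (reduced). SD is 1 at each time. Correlations are 0.5, 0.354 and 0.25 at gaps of 4, 8 and 12 weeks. Two-sided 0.05 is assumed.

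**2. The plan's own power.** A repeated measures ANOVA with a Geisser-Greenhouse correction gives 84.8% for slopes at 15 per group (stated 85%) and 94.4% at 20 per group (stated 95%). The plan reproduces. Recruiting 30 per group with 33% attrition leaves about 20, so 95% is the relevant base.

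**3. The same on per-infant slopes.** Least-squares weights are −0.075, −0.025, 0.025 and 0.075.
- Difference in slopes: 0.12125 − 0.0025 = 0.11875 mg/dL/week.
- Slope variance: 0.0125 + 2 × [0.5 × 0.003125 − 0.354 × 0.00375 − 0.25 × 0.005625] = 0.01016; SD 0.1008.
- SE at 20 per group: 0.1008 × √(2/20) = 0.0319; ratio 0.11875/0.0319 = 3.73; power 95.3% (noncentral t).

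The SD of 1 is a total SD, so this is already the power of an analysis without strata.

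**4. Which terms matter.** A generalised least squares simulation used 20 per group, 5 centres × 2 gestational-age strata (assumed), complete data and 1,500 runs. Stratum effects were added on top of the SD of 1.

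| Assumed stratum effect | Terms compared | Result |
|---|---|---|
| None | none vs main effects and gestational age × time | power 94.3% vs 94.2% |
| Level differs by 1 mg/dL | none vs main effects | spread of estimate 0.0317 both; power 95.9% vs 95.1% |
| Slope differs by 0.05 mg/dL/week (about 6% of slope variance) | none vs with gestational age × time | mean SE 0.0317 vs 0.0316; power 94.3% both |
| Slope differs by 0.10 mg/dL/week (about 20%) | none vs with gestational age × time | mean SE 0.0346 vs 0.0315; power 91.7% vs 94.3% |

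In the last row the true spread of the estimate is 0.0332 without the terms and 0.0333 with them. The estimate hardly changes; the unadjusted model overstates its SE. Main effects alone do nothing useful, because the random intercept already absorbs differences in level.

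**5. Size under an assumed range.** Let R² be the share of the variance of per-infant slope estimates explained by gestational age, within the total SD of 1. Two simulations used 4 assumed centres and 40 analysed infants: (A) 60 randomised and 40 retained; (B) 40 with complete data, 5,000 runs.

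| R² | Type I error, unadjusted (A; B) | Power at planned effect, unadjusted → adjusted (A; B) | Power at 70% of it (A; B) |
|---|---|---|---|
| 10% | 0.049; 0.042 | 95 → 96; 95.5 → 96.4 | 71 → 75; 72 → 76 |
| 20% | 0.037; 0.033 | 96 → 98; 96.2 → 98.1 | 73 → 80; 73 → 80 |
| 30% | 0.029; 0.028 | 97 → 99; 96.9 → 99.1 | 72 → 85; 74 → 86 |

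Gains at the planned effect are 1 to 2 points here (2.6 in step 4). At 70% of it they are 4, 7 and 12 to 13 points. Adjusted type I error in B was 0.051, 0.053 and 0.057, with Monte Carlo error √(0.05 × 0.95/5000) ≈ 0.003.

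**6. Limiting case.** With exact balance within strata, α = 2 × [1 − Φ(1.96/√(1 − R²))] gives 0.039, 0.028 and 0.019. Small incomplete blocks and attrition make the real conservatism milder, as in step 5.

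**The case against.** The strongest reply is that nothing in the documents shows the bilirubin slope to differ by gestational age or centre. The Background names prematurity as a risk factor for developing PNAC, not for a steeper slope. Eligibility also narrows the range: at least 28 weeks corrected gestational age at enrolment, and birthweight under 1 kg excluded. This stands, and it makes the loss conditional.

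A reader might infer that the standard error is certainly too wide and that planned power is lost. The documents do not support that. The contrast is arm by time, the random intercept takes up differences in level, and the sample size claims no benefit from stratifying. Nor is 85% the right base; that figure is for 15 per group.

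The meaning of R² also matters. A random-slope fit to the stated correlations at four visits puts true between-infant slope variance at about 0.0042 of 0.0102, or 41%. If the 10% to 30% referred to that part only, the exact-balance α would be about 0.045, 0.041 and 0.036. Weekly sampling would raise the 41%.

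Finally, random centre slopes may not be estimable with 60 infants and an unstated number of centres. This stands too, and it limits the fix. None of these points gives a reason to leave gestational age out of the primary model when it is used in the growth model.

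**Conclusion.** The mismatch between design and primary analysis is real, and its consequence is modest and conditional. If slopes differ by gestational-age stratum, the unadjusted test is conservative and the interval wider than needed. For an R² of 10% to 30%, type I error is about 0.05 down to 0.03. Adjustment is worth about 1 to 3 points of power at the planned effect and about 4 to 12 points at 70% of it, so it helps most if the near-zero slope assumed for the reduced arm proves optimistic. If slopes do not differ, it makes essentially no difference.

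False positives are not inflated, and power stays at or above the planned 95% with 20 evaluable per group. That last statement rests on reading the SD of 1 as a total SD, as the plan presents it. If stratum variance came on top, unadjusted power could be nearer 92%, as in the last row of step 4. The other assumptions are two-sided testing, 4 or 5 centres and complete data on the analysed infants.

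**What to change.** Add one sentence to Primary Outcome Measure, settled before unblinding: the linear mixed model will include the gestational-age stratum (<32 vs ≥32 weeks) and its interaction with time as fixed effects. The interaction is the part that matters, because the treatment effect is itself an arm-by-time term.

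Centre may be added as a random intercept; a random centre slope should not be required. If centre is left out, say so and give the reason.

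The cost is two fixed-effect parameters. Gestational age is already recorded for randomisation, and no extra infants, visits or samples are needed.
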